## 5. Analysis Datasets

Population	Definition / Criteria	Analyses Evaluated
Screened	

• All participants who were screened for eligibility

	

• Study population

Enrolled	

• All participants who passed screening (met eligibility criteria) and entered the study.

• Note screening failures (who never passed screening even if rescreened) and participants screened but never enrolled into the study are excluded from the Enrolled population as they did not enter the study.

	

• Study population

• Primary analysis

• Secondary analysis

• Safety analysis

 
CCI [REDACTED]

## 6. Statistical Methods

### 6.1. General Statistical Consideration

Demographics and baseline characteristics data, primary data, secondary data, CCI [REDACTED] and safety data will be analyzed. CCI [REDACTED]  
[REDACTED]

The final planned primary analyses will be performed after the completion of the following sequential steps:

- All participants have completed the study as defined in the protocol.
- All required database cleaning activities have been completed and final database release (DBR) and database freeze (DBF) has been declared by Data Management.

#### 6.1.1. Reporting Process

Software

• The SAS 9.4 version or above software will be used.

Analysis Datasets

• Analysis datasets will be created according to Tigermed's standards

Generation of RTF Files

• Both RTF and PDF files will be generated.

#### 6.1.2. Reporting Standards

General

• Tigermed's template will be applied for reporting, unless otherwise stated.

Formats	

For continuous data, min and max are rounded to the same decimal place as the original data; mean, median, Q1 and Q3 are rounded to one decimal place more than the original data; SD are rounded to two decimal places more than the original data. All above statistics will be rounded to no more than 4 decimal places.

For categorical data, percentage is rounded to 1 decimal place. If CI is needed, the lower and upper bounds will be rounded to 2 decimal places.

P value will be rounded to 4 decimal places. '<.0001' will be displayed when the P value is lesser than 0.0001 and '>.9999' will be displayed when the P value is greater than 0.9999.

	
Unscheduled Visits	

Unscheduled visits will not be included in summary tables and figures.

All unscheduled visits will be included in listings.

	
Descriptive Summary Statistics	
Continuous Data	number of non-missing subjects (n), number of missing patients (nmiss), mean, standard deviation (SD), median, 25% quantile (Q1), 75% quantile (Q3), minimum (min) and maximum (max)
Categorical Data	N, n, frequency, %
Statistical test whenever required	
Continuous Data	T test, ANOVA, Wilcoxon rank sum test or Wilcoxon signed-rank test
Categorical Data	Chi-square test, Fisher's exact test
Model Selection	

Logistic regression

 
The covariates with P-value less than 0.1 in univariate logistic regression and fixed variables (including Age, Gold grade, Baseline CAT score, Type of hospital and History of exacerbation) will be included in the multivariate logistic regression model.
	
Significance of test	

Statistical analysis will be performed under the bilateral significance level of 0.05 whenever required, unless otherwise specified.

	

### 6.1.3. Baseline Definitions

The measurement at baseline visit will be defined as baseline, unless otherwise specified. If the patient is too ill, then baseline data will be collected before discharge. Unless otherwise stated, if baseline data is missing no derivation will be performed and baseline will be set to missing.

Definition	Reporting Details
Change from Baseline	= Post-baseline Value – Baseline
% Change from Baseline	= $100 \times [(Post\text{-}baseline\ Value - Baseline) / Baseline]$

### 6.1.4. Multicenter Studies

It is estimated that 750 patients each from tier 2 and tier 3 hospitals will be enrolled to provide

adequate representation on healthcare status for COPD in China. All analyses of primary, secondary [REDACTED] will be performed for Tier 2 and 3 hospitals separately.

### 6.1.5. Covariates and Other Strata

The list of covariates and other strata may be used in descriptive summaries and statistical analyses, some of which may also be used for subgroup analyses. Additional covariates and other strata of clinical interest may also be considered.

Covariates	Details
Age	below 65 years old 65 years old and above
Gender	female male
Smoking history	Never smoking Used to smoke Current smoking
Any comorbidity	

• Cardiovascular Disease (CVD defined as ischemic heart disease, heart failure, atrial fibrillation, hypertension): yes vs no

• Diabetes: yes vs no

• Hyperlipemia: yes vs no

• Anxiety or Depression: yes vs no

• Gastroesophageal reflux disease (GERD): yes vs no

• Obstructive sleep apnea syndrome (OSAS): yes vs no

• Concurrent asthma with COPD: yes vs no

• Past history of tuberculosis: yes vs no

Baseline GOLD 2019 group	A B C D
Annual income (KRMB)	<30, 30-80, >80
Proportion of outpatient medical insurance (for COPD treatment) (%)	<33%, 33-66%, >66%
Place of residence	city vs outside city
Educational level	illiterate primary school junior mid-school high-school university
Gold grade (Classification of severity of airflow limitation in	I=Mild II=Moderate

Covariates	Details
CRF)	III=Severe IV=Very severe
mMRC	Grade 0, Grade 1, Grade 2, Grade 3, Grade 4
Baseline CAT score	$\leq 10, 11-20, 21-30, 31-40$ . And it will be as continuous data in Logistic regression.
Type of hospital	Tier 2, Tier 3
History of exacerbation	None, Moderate exacerbation, Previous hospitalised exacerbation; And two level (none and exacerbation) will be used in Logistic regression.
Severity of exacerbation (only for exacerbation cohort)	Mild, Moderate, Severe

### 6.1.6. Examination of Subgroups

The list of subgroups may be used in descriptive summaries and statistical analyses. Additional subgroups of clinical interest may also be considered.

Subgroup	Categories
Disease status at baseline	stable exacerbation
Exacerbation status at baseline	moderate exacerbation, requiring hospitalization for an exacerbation
DECAF risk	Mild(0-1 score), moderate(2 score) and severe(3-6 score)
Treatment satisfaction	Satisfied with current treatment overall: yes vs no
Treatment confidence	More optimistic, very pessimistic and lost confidence, no strong feelings
Level of physical activities(IPAQ)	Low, moderate and high
Level of depression(PHQ9)	None-minimal(0-4 score), mild(5-9 score), moderate(10-14), moderately severe(15-19 score), severe(20-27 score)
Smoke	$\geq 10$ pack year vs $< 10$ pack year

### 6.1.7. Multiple Comparisons and Multiplicity

Analyses of endpoints will not be subject to any multiplicity adjustment.

## 6.2. Data Handling

### 6.2.1. Premature Withdrawal and Missing Data

#### ➤ Premature Withdrawals

Element	Reporting Detail
General	

Subject study completion (i.e. as specified in the protocol) was defined as completion of all phases of the study.

Withdrawn subjects will not be replaced in the study.

All available data from participants who were withdrawn from the study will be listed and all available planned data will be included in summary tables and figures, unless otherwise specified.

➤ **Handling of Missing Data and Outliers**

Element	Reporting Detail
Missing Data	

Missing data occurs when any requested data is not provided, leading to blank fields on the collection instrument:

These data will be indicated by the use of a “blank” in subject listing displays. Unless all data for a specific visit are missing in which case the data is excluded from the table.

Answers such as “Not applicable” and “Not evaluable” are not considered to be missing data and should be displayed as such.

Outliers	

Any participants excluded from the summaries and/or statistical analyses will be documented along with the reason for exclusion in the clinical study report.

➤ **Handling of Missing and Partial Dates**

Element	Reporting Detail
General	

Partial dates will be displayed as captured in subject listing displays.

Adverse Events	

The eCRF allows for the possibility of partial dates (i.e., only month and year) to be recorded for AE start and end dates; that is, the day of the month may be missing.

Completely missing start or end dates will remain missing, with no imputation applied. Consequently, time to onset and duration of such events will be missing.

The recorded partial date will be displayed in the listings

Concomitant Medications/ Medical History	

Partial dates for any concomitant medications recorded in the CRF will not be imputed.

The recorded partial date will be displayed in listings.

**6.2.2. Derivation and Transformation on Data**

Baseline GOLD 2019 group
A: 0 or 1 exacerbation (not leading to hospital admission) and (CAT <10)
B: 0 or 1 exacerbation (not leading to hospital admission) and (CAT $\geq$ 10)

C: $\geq 2$ exacerbations or 1 exacerbation leading to hospital admission and (or CAT <10) D: $\geq 2$ exacerbations or 1 exacerbation leading to hospital admission and (CAT $\geq 10$ )
Level of physical activities(IPAQ) See Appendix 3 for details.
Level of depression(PHQ9) See Appendix 4 for details.
Body Mass Index (BMI) 

Calculated as Weight (kg) / [Height (m)], rounded to 1 decimal place. BMI<18.5 underweight, 18.5<math>\leq</math> BMI<24 normal, 28>BMI<math>\geq</math>24 overweight, BMI<math>\geq</math>28 obesity

Days from enrolled date to completion or prematurely withdrew of the study 

Calculated as completion or early termination date – enrolled date + 1

Duration of COPD (months) 

(Calculated as enrolled date –COPD diagnosis date+1) <math>\div</math> 30.4375 days, round to 2 decimal places.

 
If only the day of COPD diagnosis date is missing: Duration of COPD (months) = (the year of enrolled date – the year of COPD diagnosis date) <math>\times</math> 12+ (the month of enrolled date – the month of COPD diagnosis date).
 
If the day and month of COPD diagnosis date are missing: Duration of COPD (months) = (the year of enrolled date – the year of COPD diagnosis date) <math>\times</math> 12.
 
If COPD diagnosis date is completely missing: duration of COPD is not calculated.

Annual income(KRMB) 

(Q6 + Q7)/1000, rounded to 3 decimal place.

 
Patient survey and questionnaire: Q6: In the past 12 months, the total income of your family (you and your spouse) was **** RMB? Q7: In the past 12 months, the total economic support you have received from your children or others was ****RMB ?

Proportion of outpatient medical insurance (for total medical treatment) (%) (total cost of medical treatment(Q8) -actual total cost(Q8))/ total cost of medical treatment (Q8) $\times$ 100, rounded to 1 decimal place. 
Patient survey and questionnaire: Q8: In the past 12 months, the total cost of your medical treatment was****RMB? After reimbursement from insurance (if any), the actual total cost was ****RMB?

Proportion of outpatient medical insurance (for COPD treatment) (%) (total cost of medical treatment(Q9) -actual total cost(Q9))/ total cost of medical treatment (Q9) $\times$ 100, rounded to 1 decimal place. 
Patient survey and questionnaire:

Q9: In the past 12 months, the total cost of your COPD treatment was\*\*\*\*RMB? After reimbursement from insurance (if any), the actual total cost was\*\*\*\*RMB?

### 6.3. Subject Disposition

The study population analyses will be based on the enrolled population, unless otherwise specified.

Study population analyses include analyses of participant's disposition, protocol deviations, demographic and baseline characteristics, COPD exacerbation history, co-morbid diseases and concomitant medications. The summary will be displayed by different cohorts and "Total".

#### 6.3.1. Subject's Disposition

The number of subjects included in screening population, those included in enrollment and reasons for screening failure will be summarized.

The number and percentage of subjects who completed the study as well as subjects who withdrew prematurely from the study will be summarized by completion status and reason for withdrawal. A listing of the subjects who withdrew from the study prematurely will be provided.

The subject's disposition analyses will be performed for Tier 2 and 3 hospitals separately.

#### 6.3.2. Protocol Deviation

Important protocol deviations (including deviations related to study inclusion/exclusion criteria, conduct of the trial, patient management or patient assessment) will be summarized. A separate summary and listing of all inclusion/exclusion criteria deviations will also be provided. This summary will be based on data as recorded on the inclusion/exclusion page of the eCRF.

All protocol deviations will be listed.

### 6.4. Demographics and Baseline Characteristics

The summary will be displayed by different cohorts and "Overall", and will also be performed for Tier 2 and 3 hospitals separately.

#### 6.4.1. Demographic characteristics

Demographic characteristics listed below will be summarized either with descriptive statistics for continuous variables or with frequencies and percentages for categorical variables.

- Continuous variables: Height, Weight, Age, BMI
- Categorical Variables: Age( below 65 years old vs. 65 years old and above), Body mass index (BMI, BMI<18.5 underweight, 18.5≤BMI<24 normal, 28>BMI≥24 overweight, BMI≥28 obesity), Gender

#### 6.4.2. Baseline socio-economic characteristics

- Continuous variables: annual income, total cost of medical treatment, total cost of COPD treatment, out-of-pocket health expenditure, out-of-pocket COPD expenditure, proportion of outpatient medical insurance.
- Categorical Variables: education, living area, marriage condition, with whom usually live, national basic medical insurance, commercial insurance.

#### 6.4.3. Substance Use

- Continuous variables: the number of pack years for former smoker and current smoker.
- Categorical Variables: smoking status, the number of pack years for former smoker and current smoker ( $\geq 10$  pack year vs  $< 10$  pack year).

#### 6.4.4. Disease severity characteristics

- Continuous variables: DECAF score, CAT score, FVC, FEV1, FEV1%pred, FEV1/FVC.
- Categorical Variables: DECAF score (mild, moderate and severe), CAT score ( $\leq 10$ , 11-20, 21-30, 31-40), mMRC score (Grade 0, Grade 1, Grade 2, Grade 3 and Grade 4), Baseline GOLD 2019 group (A, B, C and D), GOLD grade (I, II, III and IV).

Variables with multiple visit should be described by visits and calculated the change from baseline.

#### 6.4.5. Questionnaire

- Continuous variables: IPAQ, PHQ9 score, GSE score.
- Categorical variables: IPAQ, PHQ9 score.

Variables with multiple visit should be described by visits and calculated change from baseline.

#### 6.4.6. COPD exacerbation history

- Duration of COPD (months), exacerbated in the past 12 months to the present (yes vs no), total frequency of exacerbations in previous 12 month, frequency of hospitalization due to exacerbation in previous 12 month.

#### 6.4.7. Co-morbid diseases

Co-morbid diseases: Cardiovascular Disease (CVD defined as ischemic heart disease, heart failure, atrial fibrillation, hypertension), Diabetes, Hyperlipemia, Anxiety, Depression, Gastroesophageal reflux disease (GERD), obstructive sleep apnea syndrome (OSAS), concurrent asthma with COPD, past history of tuberculosis.

Number and percentage of patients who had each co-morbid diseases will be summarized using descriptive statistics. All disease name will also be summarized by System Organ Class (SOC) and preferred term (PT) that will be coded using the latest version of MedDRA. If a patient has more than one record in a relevant category, the patient will be counted only once for the category. The summary will be sorted in decreasing order of occurrence rate of SOC firstly and then sorted in decreasing order of occurrence rate of PT.

Detailed information of co-morbid diseases will be listed by patient.

## 6.5. Treatment Compliance and Concomitant Medication

### 6.5.1. Treatment Compliance

See section 6.7 for more details about the change of COPD prescription for maintenance.

### 6.5.2. Concomitant Medications

The CRF texts for concomitant medications will be coded using the WHO Drug Dictionary. A by-subject listing of concomitant medications using generic term will be provided.

## 6.6. Primary Analysis

### 6.6.1. Primary Analysis

#### ➤ Endpoint / Variables

The COPD prescription for maintenance therapy at each visit.

#### ➤ Summary Measure

The number and percentage of patients who receive any maintenance treatment prescription at each visit will be summarized.

The number and percentage of patients who receive different pattern of the maintenance treatment prescription at each visit. The categories will be binary, e.g. treatment class used: Yes/No.

The above analyses will also be performed for Tier 2 and 3 hospitals separately.

#### ➤ Population of Interest

The primary analyses will be based on the enrolled population.

#### ➤ Statistical Analyses / Methods

The number and percentage of patients who receive the maintenance treatment prescription 1/2/3 at each visit will be summarized. Moreover, for those who receive the maintenance treatment prescription, the number and percentage of patients will be summarized for each of the following pattern of maintenance treatment prescription:

- Long-Acting Muscarinic Antagonist [LAMA]
- Long-Acting Beta-Agonist [LABA]
- Dual bronchodilator [LABA/LAMA]
- Inhaled corticosteroid [ICS]/ Long-Acting Beta-Agonist [LABA]
- Triple therapy [ICS/LABA/LAMA, SITT]

- MITT
- Theophylline
- MITT or SITT
- N-acetyl cysteine/carbocysteine

The maintenance treatment prescription: including LAMA, LABA, LABA/LAMA, ICS/LABA, SITT, MITT, Theophylline, MITT or SITT, N-acetyl cysteine/carbocysteine.

The inhaler maintenance treatment prescription: including LAMA, LABA, LABA/LAMA, ICS/LABA, SITT, MITT, Theophylline.

The oral maintenance treatment prescription: including Theophylline, N-acetyl cysteine/carbocysteine.

If the patient received both LAMA and ICS/LABA at the same visit, the patient's pattern of maintenance treatment prescription was MITT, and the treatment pattern could not be identified as either LAMA or ICS/LABA.

The results for patients with stable disease and patients with exacerbation at baseline will be analyzed separately for the following visits: baseline visit, 1-week follow up (for moderate exacerbations) and discharge follow-up (for hospitalized exacerbations).

The results for patients with stable disease and patients with exacerbation will be pooled together for analysis for 3-month follow-up visit. The percentage will be compared between stable and exacerbating patients by maintenance treatment.

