### **Statistical Methodology Specification**

Endpoint / Variables

• The COPD prescription for maintenance therapy at each visit

Model Specification

• Chi-square test or Fisher's exact test

• Bonferroni-corrected P value will be calculated when the P value of Chi-square test or Fisher's exact test is less than 0.05.

Model Checking & Diagnostics

• N/A

Model Results Presentation

• The number and percentage of patients who receive any maintenance treatment prescription will be reported.

• The number and percentage of patients who receive different pattern of the maintenance treatment prescription will be reported separately.

• The P value will be reported.

Subgroup Analyses
• N/A
Sensitivity Analyses
• N/A
Supportive Analyses
• N/A

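### SAP 6.6.1 lists theophylline under both inhaler and oral maintenance, so a patient on theophylline with no inhaled class counts as receiving inhaler maintenance

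*SAP*

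**What the plan says.** SAP section 6.6.1, under Statistical Analyses / Methods, gives three group definitions in succession:

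- All maintenance: "The maintenance treatment prescription: including LAMA, LABA, LABA/LAMA, ICS/LABA, SITT, MITT, Theophylline, MITT or SITT, N-acetyl cysteine/carbocysteine".
- Inhaler: "The inhaler maintenance treatment prescription: including LAMA, LABA, LABA/LAMA, ICS/LABA, SITT, MITT, Theophylline".
- Oral: "The oral maintenance treatment prescription: including Theophylline, N-acetyl cysteine/carbocysteine".

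The same subsection opens with "The number and percentage of patients who receive the maintenance treatment prescription 1/2/3 at each visit will be summarized". The label 1/2/3 is not defined. Percentages for the individual classes then follow, restricted to treated patients: "for those who receive the maintenance treatment prescription, the number and percentage of patients will be summarized". The analysis set is stated separately: "The primary analyses will be based on the enrolled population".

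The only reassignment rule in 6.6.1 turns LAMA plus ICS/LABA at the same visit into MITT. There is no rule for theophylline. Protocol section 5.1 lists theophylline as a class of its own and has no inhaler or oral grouping. SAP section 9, which records changes from the protocol, does not mention these groups.

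**The concern.** The two group labels name a route of administration, and apart from theophylline the lists share no entry: N-acetyl cysteine/carbocysteine is oral only, and the six bronchodilator and ICS classes are inhaler only. The SAP itself calls theophylline oral, and neither document describes an inhaled form. Its presence in the inhaler list therefore looks like a drafting slip, but it is written as a rule that a programmer would follow.

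The study exists to quantify prescribing patterns, so its class definitions are its measuring instrument. An inhaler row built from this list would overstate inhaled treatment. The error runs in one direction and does not shrink with sample size. If use of theophylline without an inhaled class differs between hospital tiers, or between stable and exacerbating patients, a comparison of inhaler percentages would be distorted too. The documents do not say whether it differs.

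The list also sits awkwardly beside SAP section 6.7.2, where the change categories rest on LAMA, LABA and ICS alone. A patient who moves from LAMA to theophylline alone is classed as stopped there, yet is still on inhaler maintenance under 6.6.1.

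**Working it through.** The plan gives no figure on this point to reproduce. The check is one of set membership, followed by simple arithmetic.

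**Step 1: overlap.** The inhaler list has seven members and the oral list has two. Their intersection is theophylline and nothing else.

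**Step 2: classification, with classes coded Yes/No as the SAP states.**

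| Prescribed | Inhaler, as written | Oral, as written | Inhaler, theophylline removed |
|---|---|---|---|
| Theophylline only | Yes | Yes | No |
| N-acetyl cysteine/carbocysteine only | No | Yes | No |
| Theophylline plus N-acetyl cysteine/carbocysteine | Yes | Yes | No |
| LAMA only | Yes | No | Yes |

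**Step 3: size of the excess.** As written, a patient is in the inhaler group if he or she has any of the six other classes or has theophylline. Hence

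excess = P(theophylline and none of the six other classes) = s.

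On the enrolled denominator the excess is s. On the any-maintenance denominator it is s/m, where m is the proportion with any maintenance prescription. For example, s = 5% and m = 80% give 0.05/0.80 = 6.25 points. The number of patients misclassified is s × n.

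Inputs: n = 375 (one patient group in one tier) and n = 1500 (total) come from protocol section 4. The documents give neither s nor m, so both are assumed: s from 0 to 10%, and m of 80% or 60%.

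| s | Points, enrolled | Points, m = 80% | Points, m = 60% | Patients of 375 | Patients of 1500 |
|---|---|---|---|---|---|
| 0% | 0 | 0 | 0 | 0 | 0 |
| 1% | 1 | 1.25 | 1.7 | 4 (3.75) | 15 |
| 2% | 2 | 2.5 | 3.3 | 8 (7.5) | 30 |
| 5% | 5 | 6.25 | 8.3 | 19 (18.75) | 75 |
| 10% | 10 | 12.5 | 16.7 | 38 (37.5) | 150 |

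**Step 4: what does not move.** Theophylline belongs to the all-maintenance list and the oral list in any case, so those two percentages are the same before and after the correction. The count for each class is also unchanged, and so is its percentage on either denominator above. The change categories in 6.7.2 do not use theophylline.

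**The case against.** The strongest reply is that the visible text never plainly promises an inhaler percentage. The summary measures in 6.6.1 are any maintenance, "The number and percentage of patients who receive any maintenance treatment prescription will be reported", and the individual patterns, "The number and percentage of patients who receive different pattern of the maintenance treatment prescription at each visit"; inhaler maintenance is not one of the nine patterns listed. The label 1/2/3 could refer to something else, and the table shells and dataset specification are separate documents that cannot be checked here. This stands as a limit on what can be claimed about reported results. However, exactly three groups are defined in the same subsection as the label, and the inhaler and oral definitions have no other evident use in the text that can be read.

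Second, the restriction to treated patients introduces the listed patterns, so textual support for an inhaler percentage on the any-maintenance denominator is thin. That is fair. The m = 80% and m = 60% columns are illustrations, and the enrolled column is the better supported one.

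Third, on that denominator the size only restates the assumed share, which may be zero. That is also true: the documents allow a formula, not an estimate.

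Fourth, if the treated-patient restriction were applied within each of the three groups, the inhaler group would become a denominator and class percentages within it would move. The text does not settle this, and part of the SAP after section 6.7 is redacted, so the statement that little else is affected holds for the visible text only.

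None of this removes the overlap, or shows that a patient on theophylline without an inhaled class belongs in a group labelled inhaler.

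**Conclusion.** The concern holds. As written, SAP 6.6.1 puts every theophylline patient in the inhaler group, including those with no inhaled class, and nothing elsewhere in the documents corrects this. The resulting inhaler percentage is too high by the share of theophylline patients without an inhaled class, taken on the same denominator: 0 to 10 points on the enrolled denominator if that share is 0 to 10%, which is an assumption. The classification error is certain from the text. Its effect on a reported number depends on the inhaler group being tabulated, which is inferred.

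The matter is confined to a descriptive grouping added in the SAP and does not touch the protocol's own primary analysis. It should be corrected all the same, because a programmer must otherwise either produce a mislabelled row or depart silently from the SAP.

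**What to change.** In SAP 6.6.1, delete theophylline from the inhaler list and keep it under oral only. In the same place, state that 1/2/3 means the all, inhaler and oral maintenance prescriptions, or whatever else is intended. If the overlap was deliberate, say so in one sentence and rename the group so that it no longer claims to be inhaler treatment. Check that the table shells and dataset specification use the corrected list.

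The cost is one word deleted and one clarifying phrase. No new data and no protocol change are needed.
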